8.2.4. Clinical Safety Laboratory Assessments

See [Appendix 2](#) for the list of clinical safety laboratory tests to be performed and the **SoA** for the timing and frequency. All protocol-required laboratory assessments, as defined in [Appendix 2](#), must be conducted in accordance with the laboratory manual and the **SoA**. Unscheduled clinical laboratory measurements may be obtained at any time during the study to assess any perceived safety issues.

The investigator must review the laboratory report, document this review, and record any clinically relevant changes occurring during the study in the AE section of the CRF. Clinically significant abnormal laboratory findings are those which are not associated with the underlying disease, unless judged by the investigator to be more severe than expected for the participant's condition.

All laboratory tests with values considered clinically significantly abnormal during participation in the study or within 28 days after the last dose of study intervention should be repeated until the values return to normal or baseline or are no longer considered clinically significant by the investigator or medical monitor.

If such values do not return to normal/baseline within a period of time judged reasonable by the investigator, the etiology should be identified and the sponsor notified.

See [Appendix 6](#) for suggested actions and follow-up assessments in the event of potential drug-induced liver injury.

Participants may undergo random urine drug testing at the discretion of the investigator. Drug testing conducted prior to dosing must be negative for participants to receive study intervention.

8.2.5. COVID-19 specific assessments

Participants will be tested for SARS-COVID-19 infection by PCR at screening and at the time of being admitted to the clinic for confinement. Additional testing may be required by local regulations or by the Principal Investigator.

8.3. Adverse Events, Serious Adverse Events, and Other Safety Reporting

The definitions of an AE and an SAE can be found in [Appendix 3](#).

AEs may arise from symptoms or other complaints reported to the investigator by the participant (or, when appropriate, by a caregiver, surrogate, or the participant's legally authorized representative), or they may arise from clinical findings of the Investigator or other healthcare providers (clinical signs, test results, etc.).

The investigator and any qualified designees are responsible for detecting, documenting, and recording events that meet the definition of an AE or SAE and remain responsible to pursue and obtain adequate information both to determine the outcome and to assess whether the event meets the criteria for classification as an SAE or caused the participant to discontinue the study (see [Section 7.1](#)).

During the active collection period as described in Section 8.3.1, each participant will be questioned about the occurrence of AEs in a nonleading manner.

In addition, the investigator may be requested by Pfizer Safety to obtain specific follow-up information in an expedited fashion.

8.3.1. Time Period and Frequency for Collecting AE and SAE Information

The time period for actively eliciting and collecting AEs and SAEs (“active collection period”) for each participant begins from the time the participant provides informed consent, which is obtained before the participant’s participation in the study (ie, before undergoing any study-related procedure and/or receiving study intervention), through and including a minimum of 28 calendar days, except as indicated below, after the last administration of the study intervention.

Follow-up by the investigator continues throughout and after the active collection period and until the AE or SAE or its sequelae resolve or stabilize at a level acceptable to the investigator.

For participants who are screen failures, the active collection period ends when screen failure status is determined.

If the participant withdraws from the study and also withdraws consent for the collection of future information, the active collection period ends when consent is withdrawn.

If a participant permanently discontinues or temporarily discontinues study because of an AE or SAE, the AE or SAE must be recorded on the CRF and the SAE reported using the CT SAE Report Form.

Investigators are not obligated to actively seek information on AEs or SAEs after the participant has concluded study participation. However, if the investigator learns of any SAE, including a death, at any time after a participant has completed the study, and he/she considers the event to be reasonably related to the study intervention, the investigator must promptly report the SAE to Pfizer using the CT SAE Report Form.

8.3.1.1. Reporting SAEs to Pfizer Safety

All SAEs occurring in a participant during the active collection period as described in [Section 8.3.1](#) are reported to Pfizer Safety on the CT SAE Report Form immediately upon awareness and under no circumstance should this exceed 24 hours, as indicated in [Appendix 3](#). The investigator will submit any updated SAE data to the sponsor within 24 hours of it being available.

8.3.1.2. Recording Nonserious AEs and SAEs on the CRF

All nonserious AEs and SAEs occurring in a participant during the active collection period, which begins after obtaining informed consent as described in [Section 8.3.1](#), will be recorded on the AE section of the CRF.

The investigator is to record on the CRF all directly observed and all spontaneously reported AEs and SAEs reported by the participant.

Reporting of AEs and SAEs for participants who fail screening are participant to the CRF requirements as described in [Section 5.4](#).

8.3.2. Method of Detecting AEs and SAEs

The method of recording, evaluating, and assessing causality of AEs and SAEs and the procedures for completing and transmitting SAE reports are provided in [Appendix 3](#).

Care will be taken not to introduce bias when detecting AEs and/or SAEs. Open-ended and nonleading verbal questioning of the participant is the preferred method to inquire about AE occurrences.

8.3.3. Follow-Up of AEs and SAEs

After the initial AE or SAE report, the investigator is required to proactively follow each participant at subsequent visits/contacts. For each event, the investigator must pursue and obtain adequate information until resolution, stabilization, the event is otherwise explained, or the participant is lost to follow-up (as defined in [Section 7.3](#)).

In general, follow-up information will include a description of the event in sufficient detail to allow for a complete medical assessment of the case and independent determination of possible causality. Any information relevant to the event, such as concomitant medications and illnesses, must be provided. In the case of a participant death, a summary of available autopsy findings must be submitted as soon as possible to Pfizer Safety.

Further information on follow-up procedures is given in [Appendix 3](#).

8.3.4. Regulatory Reporting Requirements for SAEs

Prompt notification by the investigator to the sponsor of an SAE is essential so that legal obligations and ethical responsibilities toward the safety of participants and the safety of a study intervention under clinical investigation are met.

The sponsor has a legal responsibility to notify both the local regulatory authority and other regulatory agencies about the safety of a study intervention under clinical investigation. The sponsor will comply with country-specific regulatory requirements relating to safety reporting to the regulatory authority, IRBs/ECs, and investigators.

Investigator safety reports must be prepared for SUSARs according to local regulatory requirements and sponsor policy and forwarded to investigators as necessary.

An investigator who receives SUSARs or other specific safety information (eg, summary or listing of SAEs) from the sponsor will review and then file it along with the SRSD(s) for the study and will notify the IRB/EC, if appropriate according to local requirements.

8.3.5. Environmental Exposure, Exposure During Pregnancy or Breastfeeding, and Occupational Exposure

Environmental exposure, occurs when a person not enrolled in the study as a participant receives unplanned direct contact with or exposure to the study intervention. Such exposure may or may not lead to the occurrence of an AE or SAE. Persons at risk for environmental exposure include healthcare providers, family members, and others who may be exposed. An environmental exposure may include exposure during pregnancy, exposure during breastfeeding, and occupational exposure.

Any such exposure to the study intervention under study are reportable to Pfizer Safety within 24 hours of investigator awareness.

8.3.5.1. Exposure During Pregnancy

An EDP occurs if:

- A male participant who is receiving or has discontinued study intervention exposes a female partner prior to or around the time of conception.

- A female is found to be pregnant while being exposed or having been exposed to study intervention due to environmental exposure. Below are examples of environmental EDP:
 - A male family member or healthcare provider who has been exposed to the study intervention by ingestion, inhalation, or skin contact then exposes his female partner prior to or around the time of conception.

The investigator must report EDP to Pfizer Safety within 24 hours of the investigator's awareness, irrespective of whether an SAE has occurred. The initial information submitted should include the anticipated date of delivery (see below for information related to termination of pregnancy).

- If EDP occurs in a participant or a participant's partner, the investigator must report this information to Pfizer Safety on the CT SAE Report Form and an EDP Supplemental Form, regardless of whether an SAE has occurred. Details of the pregnancy will be collected after the start of study intervention and until 28 days after the last dose.
- If EDP occurs in the setting of environmental exposure, the investigator must report information to Pfizer Safety using the CT SAE Report Form and EDP Supplemental Form. Since the exposure information does not pertain to the participant enrolled in the study, the information is not recorded on a CRF; however, a copy of the completed CT SAE Report Form is maintained in the investigator site file.

Follow-up is conducted to obtain general information on the pregnancy and its outcome for all EDP reports with an unknown outcome. The investigator will follow the pregnancy until completion (or until pregnancy termination) and notify Pfizer Safety of the outcome as a follow-up to the initial EDP Supplemental Form. In the case of a live birth, the structural integrity of the neonate can be assessed at the time of birth. In the event of a termination, the reason(s) for termination should be specified and, if clinically possible, the structural integrity of the terminated fetus should be assessed by gross visual inspection (unless preprocedure test findings are conclusive for a congenital anomaly and the findings are reported).

Abnormal pregnancy outcomes are considered SAEs. If the outcome of the pregnancy meets the criteria for an SAE (ie, ectopic pregnancy, spontaneous abortion, intrauterine fetal demise, neonatal death, or congenital anomaly in a live-born baby, a terminated fetus, an intrauterine fetal demise, or a neonatal death), the investigator should follow the procedures for reporting SAEs. Additional information about pregnancy outcomes that are reported to Pfizer Safety as SAEs follows:

- Spontaneous abortion including miscarriage and missed abortion;
- Neonatal deaths that occur within 1 month of birth should be reported, without regard to causality, as SAEs. In addition, infant deaths after 1 month should be reported as

SAEs when the investigator assesses the infant death as related or possibly related to exposure to the study intervention.

Additional information regarding the EDP may be requested by the sponsor. Further follow-up of birth outcomes will be handled on a case-by-case basis (eg, follow-up on preterm infants to identify developmental delays). In the case of paternal exposure, the investigator will provide the participant with the Pregnant Partner Release of Information Form to deliver to his partner. The investigator must document in the source documents that the participant was given the Pregnant Partner Release of Information Form to provide to his partner.

8.3.5.2. Exposure During Breastfeeding

An exposure during breastfeeding occurs if:

- A female is found to be breastfeeding while being exposed or having been exposed to study intervention (ie, environmental exposure). An example of environmental exposure during breastfeeding is a female family member or healthcare provider who reports that she is breastfeeding after having been exposed to the study intervention by ingestion, inhalation, or skin contact.

The investigator must report exposure during breastfeeding to Pfizer Safety within 24 hours of the investigator's awareness, irrespective of whether an SAE has occurred. The information must be reported using the CT SAE Report Form. When exposure during breastfeeding occurs in the setting of environmental exposure, the exposure information does not pertain to the participant enrolled in the study, so the information is not recorded on a CRF. However, a copy of the completed CT SAE Report Form is maintained in the investigator site file.

An exposure during breastfeeding report is not created when a Pfizer drug specifically approved for use in breastfeeding women (eg, vitamins) is administered in accord with authorized use. However, if the infant experiences an SAE associated with such a drug, the SAE is reported together with the exposure during breastfeeding.

8.3.5.3. Occupational Exposure

The investigator must report any instance of occupational exposure to Pfizer Safety within 24 hours of the investigator's awareness using the CT SAE Report Form regardless of whether there is an associated SAE. Since the information about the occupational exposure does not pertain to a participant enrolled in the study, the information is not recorded on a CRF; however, a copy of the completed CT SAE Report Form must be maintained in the investigator site file.

8.3.6. Cardiovascular and Death Events

Not applicable.

8.3.7. Disease-Related Events and/or Disease-Related Outcomes Not Qualifying as AEs or SAEs

Not applicable.

8.3.8. Adverse Events of Special Interest

Not applicable.

8.3.8.1. Lack of Efficacy

This section is not applicable because efficacy is not expected in the study population.

8.3.9. Medical Device Deficiencies

Not applicable.

8.3.9.1. Medication Errors

Medication errors may result from the administration or consumption of the study intervention by the wrong participant, or at the wrong time, or at the wrong dosage strength.

Exposures to the study intervention under study may occur in clinical trial settings, such as medication errors.

Safety Event	Recorded on the CRF	Reported on the CT SAE Report Form to Pfizer Safety Within 24 Hours of Awareness
Medication errors	All (regardless of whether associated with an AE)	Only if associated with an SAE

Medication errors include:

- Medication errors involving participant exposure to the study intervention;
- Potential medication errors or uses outside of what is foreseen in the protocol that do or do not involve the study participant.

Such medication errors occurring to a study participant are to be captured on the medication error page of the CRF, which is a specific version of the AE page.

In the event of a medication dosing error, the sponsor should be notified within 24 hours.

Whether or not the medication error is accompanied by an AE, as determined by the investigator, the medication error is recorded on the medication error page of the CRF and, if applicable, any associated AE(s), serious and nonserious, are recorded on the AE page of the CRF.

Medication errors should be reported to Pfizer Safety within 24 hours on a CT SAE Report Form only **when associated with an SAE**.

8.4. Pharmacokinetics

The samples collected for PK (non-radiolabeled PF-07265803 concentrations), radioactivity (total ¹⁴C) and/or metabolite profiling assessment must be processed and shipped as indicated in the instructions provided to the investigator site to maintain sample integrity. Any deviations from the sample handling procedure (eg, sample collection and processing steps, interim storage or shipping conditions), including any actions taken, must be documented and reported to the sponsor. On a case-by-case basis, the sponsor may make a determination as to whether sample integrity has been compromised. Samples collected for PK, radioactivity and/or metabolite profiling/ID may also be used to evaluate safety or efficacy aspects related to concerns arising during or after the study, for metabolite identification and/or evaluation of the bioanalytical method, or for other internal exploratory purposes. Genetic analysis will not be performed on these samples unless consent for this was included in the informed consent. Participant confidentiality will be maintained.

8.4.1. Plasma Analysis of Non-Radiolabeled PF-07265803

Blood samples of approximately 4 mL, will be collected into appropriately labeled tubes containing K₂EDTA at times specified in the [SoA](#) of the protocol to provide approximately 1.5 mL plasma, will be collected for measurement of plasma concentrations of PF-07265803 and metabolites as specified in the Bioanalytical Plan. Instructions for the collection and handling of biological samples will be provided in the laboratory manual or by the sponsor. The actual date and time (24-hour clock time) of each sample will be recorded. The concentrations of “cold” PF-07265803 will be measured by a validated LCMS method.

The actual times may change, but the number of samples will remain the same. All efforts will be made to obtain the samples at the exact nominal time relative to dosing. Collection of samples up to and including 10 hours after dose administration that are obtained within 10% of the nominal time relative to dosing (eg, within 6 minutes of a 60-minute sample) will not be captured as a protocol deviation, as long as the exact time of the collection is noted on the source document and the CRF. Collection of samples more than 10 hours after dose administration that are obtained \leq 1 hour away from the nominal time relative to dosing will not be captured as a protocol deviation, as long as the exact time of the collection is noted on the source document and the CRF. This protocol deviation window does not apply to samples to be collected more than 10 hours after dose administration at outpatient/follow-up visits with visit windows.

Samples collected for analyses of plasma concentration may also be used to evaluate safety or efficacy aspects related to concerns arising during or after the study, for metabolite identification and/or evaluation of the bioanalytical method, or for other internal exploratory purposes.

8.4.2. Metabolite Profiling/ID

8.4.2.1. Plasma for Metabolite Profiling/ID

Blood samples (10 mL) to provide plasma, will be collected into appropriately labeled tubes containing K₂EDTA at times specified in the **SoA** section of the protocol. Handling of plasma samples, including procedures to stabilize metabolites will be addressed in the Laboratory Manual.

8.4.2.2. Urine for Metabolite Profiling/ID

Urine will be collected over intervals described in the **SoA** section of the protocol. Handling of urine samples, including procedures to stabilize metabolites will be addressed in the Laboratory Manual.

- **Prior to dosing on Day 1 at any time**, each subject must empty his urinary bladder, and an aliquot from this urine will serve as the “urine blank”. Approximately 10 mL of urine will be collected predose for analysis.
- **Following dosing on Day 1**, each void post dose will be collected and saved in a container and stored in refrigerated conditions (ie, 2-8°C) for the duration of the collection interval. An aliquot of approximately 100 mL from **each collection interval** will be withdrawn for measurement of metabolite concentrations/profiling.
- At the end of the collection interval, subjects will attempt to empty bladder prior to the start of the next interval with this void included as part of the interval collection;
- **If** end of urine collection interval coincides with a meal, subjects will attempt to void **prior to initiation of the meal**; in such cases, so long as the actual time of forced void is recorded, **for practical reasons**, the fact that this collection may be more than 30-minutes (and up to 45-minutes) **prior** to end of collection interval is acceptable and will **not** be considered as protocol deviation.
- The urine container will be mixed thoroughly and total weight of the urine collected during the interval recorded

8.4.2.3. Feces for Metabolite Profiling/ID

- All feces will be collected over intervals described in the **SoA** section of the protocol. A pre-dose sample will also be collected. When feces are being collected, all toilet paper that come in contact with the subject's feces will also be collected for possible analysis in appropriately labelled containers stored at approximately -20°C. In the event of diarrhea during the study, all diarrhea including any swabbing and contaminated linen should be collected, labeled, and stored in appropriate containers at approximately -20°C for possible analysis of radioactivity. **Prior to dosing on Day 1 at any time**, each subject must complete a fecal void. A mild laxative may be used to promote a bowel movement and complete fecal void to improve radiolabel material recovery. Approximately 15 g of feces will be collected predose for analysis. **For**

each collection interval, an aliquot of 40 g will be withdrawn for metabolic identification and profiling. A mild laxative may be used to promote a bowel movement in concordance with the guidance in Section 6.8. Detailed sample handling instructions will be provided separately to the site before the start of the study.

8.4.3. Radioactivity

8.4.3.1. Sample Collection

It is extremely important to quantitatively collect all scheduled blood, urine, feces and emesis samples. The separate collection of urine and feces is critical to the success of this study. If urine and feces becomes mixed at any collection, note the weight and add the feces-contaminated urine to the feces collection. Samples missed or lost for any reason should be documented on the case report forms (CRFs).

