3. OBJECTIVES AND ENDPOINTS

Objectives	Endpoints
Primary: To characterize rate and extent of excretion of total radioactivity in urine and feces, following a single oral dose of [¹⁴ C]PF-07265803 administered to healthy adult male participants.	Primary: Mass Balance: cumulative recovery of urinary, fecal, and total excretion of radioactivity over time expressed as percentage of total radioactive dose administered.
To characterize metabolic profile and identify circulating and excreted metabolites following administration of a single oral dose of [¹⁴ C]PF-07265803 to healthy adult male participants.	Metabolic profiling/identification and determination of relative abundance of PF-07265803 and the metabolites of PF-07265803 in plasma, urine, and feces.
Secondary: To quantify plasma concentrations and pharmacokinetic parameters of PF-07265803, its known circulating metabolites (PF-07327859, PF-07327860, PF-07327890) and total radioactivity in plasma following administration of a single oral dose of [¹⁴ C]PF-07265803 to healthy adult male participants.	Secondary: Pharmacokinetic parameters AUC _{last} , AUC _{inf} , CL/F, V _z /F, C _{max} , T _{max} , and t _{1/2} to describe single dose PK of: PF-07265803 and where appropriate PF-07327859, PF-07327860, PF-07327890. Total radioactivity in plasma; PF-07265803, PF-07327859, PF-07327860 and PF-07327890 concentrations in plasma.
To evaluate safety and tolerability of a single oral dose of [¹⁴ C]PF-07265803 administered to healthy adult male participants.	Safety endpoints including physical examinations, adverse events, clinical laboratory measurements, vital signs and ECG.

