8.4.3.4. Fecal Sample Collection for Total Radioactivity

Feces will be collected over intervals described in the **SoA**. A predose aliquot of 15 g will be collected. **For each post dose collection interval**, an aliquot of 100 g will be withdrawn for total radioactivity measurements. Detailed sample handling instructions will be provided separately to the site before the start of the study and described in the Laboratory Manual.

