6.3.2. Mass Balance

Mass Balance: cumulative recovery of urinary, fecal, and total excretion of radioactivity over time expressed as percentage of total radioactive dose administered.

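### Whenever urine and feces mix, the collection rule books the urinary radioactivity as fecal, and the SAP has no step that shows or bounds the shift

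*Protocol*

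**What the plan says.** Protocol 8.4.3.1 sets out the importance of clean collection: "The separate collection of urine and feces is critical to the success of this study". It then gives the rule for when this fails: the site is to record the weight and "add the feces-contaminated urine to the feces collection". The same section asks for CRF documentation of samples that are missed or lost. It does not say where the weight of a mixed collection is recorded.

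The first primary endpoint (Protocol 3) is "cumulative recovery of urinary, fecal, and total excretion of radioactivity over time expressed as percentage of total radioactive dose administered". SAP 6.3.2 repeats it. The second primary endpoint includes "determination of relative abundance of PF-07265803 and the metabolites of PF-07265803 in plasma, urine, and feces".

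For each fecal interval, Protocol 8.4.3.4 says that "an aliquot of 100 g will be withdrawn for total radioactivity measurements", and Protocol 8.4.2.3 says that "an aliquot of 40 g will be withdrawn for metabolic identification and profiling". Urine radioactivity is measured in a 25 mL aliquot per interval (Protocol 8.4.3.3), and the total urine weight per interval is recorded (Protocol 8.4.2.2).

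SAP 8.2.2 summarizes recovery in urine, in feces and in the two combined. It has no provision for a mixed interval. The Extent of Excretion Analysis Set (SAP 5.1.3) requires evaluable urinary and fecal data and removes participants whose deviations or adverse events may have affected the analysis. It gives vomiting, diarrhea and severe constipation as examples. Mixing is not mentioned, and evaluable is not defined.

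**The concern.** The protocol foresees mixing and gives an explicit instruction for it. That instruction protects one of the three recovery figures in the primary endpoint, the total, and moves the other two in a fixed direction: urine down, feces up. An error that always has the same sign does not average out over participants.

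The metabolite endpoint is exposed as well. If the fecal collection for an interval contains urine, the 40 g profiling aliquot can carry urinary metabolites that would be reported as fecally excreted. The rate of excretion also loses detail. The SoA footnotes collect Day 1 urine over 0-6, 6-12 and 12-24 hours but feces over 24-hour periods, so an early void moved into feces loses its time interval.

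Later steps do not clearly catch this. A site that follows 8.4.3.1 has not plainly deviated from the protocol, and mixing is not an adverse event. It is therefore uncertain whether the analysis-set rule or the deviation review in SAP 5.6.2 would identify the participant.

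**Working it through.** The documents contain no figure to reproduce: no mixing rate, no expected urine/feces split, and a sample size of 6 that Protocol 9.5 says does not rest on empirical data. The check is therefore bookkeeping, with assumed inputs.

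**Notation.** U = true percentage of dose in urine; F = true percentage in feces; m = share of the participant's urinary radioactivity that lies in mixed voids.

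**Under the current rule**

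- Reported urine = U(1 − m)
- Reported feces = F + U·m
- Reported total = U + F, unchanged
- Shift between routes = U·m
- Shift in the mean of six with one participant affected = U·m / 6

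**Numbers** (m of 5% and 15% are assumptions, as is each U)

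| U | Shift at m = 5% | Shift at m = 15% | On mean of 6, one affected |
|---|---|---|---|
| 20% | 1.0 | 3.0 | 0.17 to 0.50 |
| 50% | 2.5 | 7.5 | 0.42 to 1.25 |
| 75% | 3.75 | 11.25 | 0.63 to 1.88 |

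All entries are percentage points of dose. At m = 0 every entry is zero.

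**Median.** With six participants the median gives limited protection. Take assumed urinary recoveries of 44, 47, 49, 51, 53 and 56, with median 50. If the participant at 51 has m = 5%, his value becomes 48.45 and the median (48.45 + 49)/2 = 48.73, a shift of 1.28. The mean moves by 2.55/6 = 0.43. At m = 15% his value becomes 43.35 and the median (47 + 49)/2 = 48, a shift of 2.0. If the participant at 44 is affected instead, the median does not move.

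**Chance that anyone is affected.** If each participant independently has probability p of any mixing, the chance of at least one in six is 1 − (1 − p)^6. For p = 2%, 5%, 10% and 20% this is 11%, 26%, 47% and 74%. The documents do not indicate which p applies.

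**What can be recovered after pooling.** The noted weight times the radioactivity concentration of unmixed urine from the same interval gives a rough limit on the amount transferred. This assumes similar concentrations across voids, unmixed urine in that interval, and a noted weight that refers to the contaminated urine. The mixed void's own radioactivity is not stated to be measured before pooling, so the limit cannot be checked.

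**What separate counting would give.** Let X be the radioactivity counted in the mixed material, u the recovery in unmixed urine and f the recovery in unmixed feces. The total is u + f + X, urinary recovery lies between u and u + X, and fecal recovery between f and f + X. For U = 50, F = 45, m = 15% and no fecal radioactivity in the mixed material, X = 7.5, urine is 42.5 to 50, feces 45 to 52.5 and the total 95. The current rule reports 42.5 and 52.5, one end of each range, as point values.

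**The case against.** An unseparated mixture has no correct route. Booking it as urine would give the opposite error and put fecal material into the urine aliquots. Pooling into feces keeps the material in the mass balance. Separate collection is the default, participants are confined, and Protocol 5.2 excludes men with irregular bowel habits, so mixing may be rare or absent. The analysis-set rule and the deviation review could remove a badly affected participant, and individual profiles are plotted. Detailed handling is deferred to separate instructions and the Laboratory Manual, which might require a count before pooling.

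Much of this stands. The effect is conditional, total recovery is protected, and neither allocation is neutral. But the last fact argues for forcing no allocation; it does not support reporting one end of the range as the value. Counting before pooling gives up nothing, because the pooled figure can still be obtained by addition. The safeguards do not name mixing, and the individual plots would not identify which intervals were mixed. The unseen manuals may add steps, but the protocol's own instruction is to pool.

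Three stronger readings are tempting. A reader might infer that this study's route split is biased; the documents cannot show that, since they give no mixing rate. A reader might infer a shift of tens of points; that needs a high urinary share together with a large fraction in mixed voids, and neither is in the documents. A reader might infer that nothing can be done after pooling; the noted weight and same-interval urine concentration do allow a rough bound.

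**Conclusion.** The point holds in conditional form. Whenever mixing occurs and the rule is followed, that participant's urinary recovery is understated and fecal recovery overstated by the urinary share of dose times the fraction of urinary radioactivity in the mixed void. Urinary metabolites can also enter the fecal profile. The combined discharge criterion in Protocol 4.1 is untouched.

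The size is unknown. The central illustration, 2.5 to 7.5 points for a participant and 0.4 to 1.25 on a mean of six, rests wholly on an assumed 50% urinary share, 5 to 15% of it in mixed voids, and one affected participant. This is an inexpensive improvement to collection and reporting. It does not show that the primary result will be wrong.

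**What to change.** **Protocol 8.4.3.1.** Keep mixed material in its own labelled container. Weigh it, count its radioactivity separately before any pooling, and record the event, interval, weight and count on the CRF. This must be in place before dosing, since a separate count is no longer possible once the material has been pooled.

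**SAP 8.2.2.** Include the amount in total recovery on its own line, 'mixed (unattributed)'. List the affected participants and intervals. Show each affected participant's urinary and fecal recovery twice, with the mixed amount assigned wholly to urine and wholly to feces.

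**Metabolite profiling.** Use unmixed feces for the interval where available. Otherwise profile the material and flag the interval as mixed. Dropping it could lose the only feces of that interval.

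**Cost.** One extra container and count per event, one table line, one listing, and short wording changes in both documents. An affected participant's route split becomes a range instead of a single value.
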